#### 5.1.2 Exclusion criteria

- Be a user of topical ophthalmic products of any kind.
- Being a user of medications or herbal products, by any other route of administration.
- In the case of women: being pregnant, breastfeeding or planning to become pregnant within of the study period.
- Have participated in clinical research studies 90 days prior to inclusion in this study
- Have previously participated in this same study.
- Be a contact lens user who cannot discontinue use during the study.
- That they cannot follow the lifestyle considerations described in section 5.3.
- Having started using hormonal contraceptives or IUDs 30 days prior to inclusion in the present study.
- Have a history of any chronic-degenerative disease.
- Present inflammatory or infectious disease, active at the time of entering the study.
- Present unresolved injuries or traumas at the time of entering the study.
- Have a history of any type of eye surgery.
- Have undergone non-ophthalmological surgical procedures in the last 3 months.
- Be or have an immediate family member (e.g., spouse, parent/legal guardian, sibling, or child) who is a research site or sponsor staff member directly involved in this study.

### 5.2 Criteria for eliminating and replacing patients

- Withdrawal of the FCI letter.
- Presentation of a serious adverse event, whether or not related to the investigational product, which, in the opinion of the PI and/or sponsor, could affect the patient's ability to safely continue study procedures.

- Non-tolerability or hypersensitivity to any of the compounds used during the tests (fluorescein, lissamine green, tetracaine).
- Non-tolerability or hypersensitivity to any of the investigational drugs.

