
Inclusion criteria:
 
 
- Be clinically healthy.
 
- Have the capacity to voluntarily grant signed informed consent.
 
- Be able and willing to comply with scheduled visits, treatment plan, and other study procedures.
 
- Be between 18 and 45 years old.
 
- Women of childbearing potential must ensure continued use (started <math>\geq</math> 30 days prior to signing the ICF) of a hormonal contraceptive method or intrauterine device (IUD) during the study period.
 
- Have corrected visual acuity (CCVA) of 20/30 or better in both eyes.
 
- Have vital signs within normal parameters.
 
- Have an intraocular pressure <math>\geq</math> 10 and <math>\leq</math> 21 mmHg.
 

Exclusion criteria:
 
 
- Be a user of topical ophthalmic products of any kind.
 
- Being a user of medications or herbal products, by any other route of administration.
 
- For women: be pregnant, breastfeeding, or planning to become pregnant during the study period.
 
- Have participated in clinical research studies 90 days prior to inclusion in this study
 
- Have previously participated in this same study.
 
- Be a contact lens user who cannot discontinue use during the study.
 
- That they cannot follow lifestyle considerations.
 
- Having started using hormonal contraceptives or IUDs 30 days prior to inclusion in the present study.
 
- Have a history of any chronic-degenerative disease.
 
- Present inflammatory or infectious disease, active at the time of entering the study.
 
- Present unresolved injuries or traumas at the time of entering the study.
 
- Have a history of any type of eye surgery.
 
- Have undergone non-ophthalmological surgical procedures in the last 3 months.
 

Research Product (RP):	

 
- PRO-172. Bepotastine 1.5% Ophthalmic Solution. Laboratorios Sophia, SA de CV Zapopan, Jalisco, Mexico.
 
- Dosage: 1 drop 4 times a day.
 
- Route of administration: Ophthalmic.
 
	
Duration of treatment:	Subject's duration in the study:
7 days	10 days
Evaluation criteria:	

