### 5.1 Eligibility criteria

#### 5.1.1 Inclusion criteria

- Be clinically healthy
- Have the ability to voluntarily grant signed informed consent
- Be able and willing to comply with scheduled visits, treatment plan, and other study procedures
- Be between 18 and 45 years old.
- Women of childbearing potential must ensure continued use (started  $\geq$  30 days prior to signing the ICF) of a hormonal contraceptive method or intrauterine device (IUD) during the study period.
- Have corrected visual acuity of 20/30 or better in both eyes.
- Have vital signs within normal parameters.
- Have an intraocular pressure  $\geq$  10 and  $\leq$  21 mmHg

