#### 7.4.1.1 Baseline Visit

- ~~Signature of the ICF~~: refers to the signing of the written informed consent document. Without informed consent, none of the study procedures can be performed.
- ~~Medical record~~: refers to the technical, clinical, and legal document that chronologically records the subject's health conditions, medical procedures, and other procedures performed on the subject. It includes anthropometric measurements, anamnesis, a comprehensive ophthalmological examination that allows determining the patient's eligibility, i.e., evaluation of both eyes and ocular adnexa, slit-lamp examination of the ocular surface and anterior segment, and fundoscopy. If the subject is taken from the study center's established population base, the existing medical record may be used; only one update is required.
- ~~Evaluation of concomitant medications~~: refers to the IP questioning the subject, inquiring about the use of medications.
- ~~Urine pregnancy test~~: This refers to a rapid pregnancy test performed on all women of childbearing age who wish to enter the study. By childbearing age, we mean women who have experienced menarche but have not yet experienced menopause. Menopause is defined as 12 months from the last menstrual period in women over 40 years of age, or who have undergone a hysterectomy or bilateral oophorectomy. Women of childbearing age using contraceptive methods, including bilateral tubal obstruction, must undergo a pregnancy test.

This test will be performed by the IP or designated team member according to the instructions on the device provided by the sponsor.

- ~~Vital signs~~: refers to heart rate, respiratory rate, systemic blood pressure, and temperature. This information must be recorded in the patient's medical history and progress notes. • ~~ccVA~~: See 7.3.3.2

---

- ~~ICQ~~: See 7.3.3.2
- ~~Ocular surface stains~~: See 7.3.3.4 and 7.3.3.5
- ~~Ophthalmological evaluation~~: See 7.3.3.1
- ~~Eligibility criteria~~: refers to the review by the PI, where it is confirmed that the subject can be included in the study by meeting the inclusion criteria and not meeting the exclusion criteria.

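### Section 5.2 eliminates subjects for hypersensitivity to PRO-172, the dyes or the anaesthetic, but no eligibility criterion excludes a volunteer already known to have it

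*Protocol*

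**What the plan says.** Protocol section 5.2, on eliminating and replacing patients, has two bullets on the point. One covers the diagnostic compounds: "Non-tolerability or hypersensitivity to any of the compounds used during the tests (fluorescein, lissamine green, tetracaine". The other covers the study treatment: "Non-tolerability or hypersensitivity to any of the investigational drugs". The study is non-comparative (6.1.2), so PRO-172 is the only investigational drug.

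Entry is governed by 8 inclusion criteria (5.1.1) and 14 exclusion criteria (5.1.2). The synopsis repeats the exclusions except the one on site or sponsor staff and their families, which leaves 13. Neither list refers to allergy, hypersensitivity or intolerance. The criteria that come nearest in subject matter are "Be clinically healthy", "Have a history of any chronic-degenerative disease" and "Present inflammatory or infectious disease, active at the time of entering the study".

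The eligibility step in 7.4.1.1 is a review by the investigator "where it is confirmed that the subject can be included in the study by meeting the inclusion criteria and not meeting the exclusion criteria". Section 8.4.1 names hypersensitivity and allergy as relevant clinical history, but only as background when an adverse event that has already happened is recorded and analysed.

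**The concern.** Sections 5.1 and 5.2 do not match. The protocol accepts that hypersensitivity to these compounds rules out continued participation, yet it does not use a known history of it at the one point where exposure could be avoided. A site that applies the listed criteria literally could enrol such a person, instil the anaesthetic and both dyes, and dispense PRO-172.

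What is at stake is the protection of subjects. They are healthy and do not have the condition the drug treats, and section 2.4.2 says the known potential benefits are not evaluated in this phase. Section 2.3.2 says the formulation has not been studied in humans before, and 11.1 classes the research as carrying more than minimum risk. Section 2.3.2 also describes bepotastine as marketed elsewhere, and the dyes and anaesthetic are not specific to this trial. A prior reaction is therefore possible, and asking about it would reveal it.

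**Working it through.** The point rests on no figure in the plan, so there is nothing to reproduce. The check is to set the eligibility text beside the elimination text.

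**1. Does a listed criterion reach a healthy person with a past reaction to one of these compounds?**

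| Criterion | Does it reach the case? |
|---|---|
| Clinically healthy (5.1.1) | No. A person with a past drug or dye reaction and no current disease can be clinically healthy. |
| Able and willing to comply with visits, treatment and procedures (5.1.1) | Arguably, by interpretation. It does not mention hypersensitivity. |
| History of chronic-degenerative disease (5.1.2) | No. A drug or dye reaction is not such a disease. |
| Inflammatory or infectious disease (5.1.2) | No. It is limited to disease active at entry. |
| Use of topical ophthalmic products, other medicines or herbal products (5.1.2) | No. It concerns use, not a past reaction. |
| Remaining criteria (age, contraception, pregnancy, visual acuity, vital signs, intraocular pressure, surgery, injury, contact lenses, lifestyle, earlier participation, staff or family) | No. |

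**2. Does another provision close the gap?** No general exclusion at the investigator's discretion is listed. Section 5.4 lets a screening failure be recorded for a reason other than an eligibility criterion, but that is a reporting category and bars nobody. The anamnesis in 7.4.1.1 may bring an allergy to light, but no criterion says what follows. The SAP sets no entry criteria.

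**3. When does exposure occur?** The suggested order in 7.4.1.1 puts the medical record, with its anamnesis, early. Ocular surface staining comes later and the eligibility review after it. Staining uses topical anaesthetic, fluorescein and lissamine green (7.3.3.4 and 7.3.3.5). The history is therefore available before the first drop, but no text requires it to be used then. Section 6.3 also permits tropicamide/phenylephrine, which 5.2 does not name. Mydriasis is optional (7.3.3.1), so this is a possible exposure, not a certain one.

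**4. Can an effect on the primary safety criterion be sized?** Section 10.1.5 requires unexpected related events in fewer than 10% of the study population.

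- With 22 subjects: 1/22 = 4.5%, 2/22 = 9.1% (meets the rule), 3/22 = 13.6% (does not).
- With the 18 subjects obtained before the allowance for losses (10.2.2): 1/18 = 5.6%, 2/18 = 11.1% (does not).

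The number of tolerated events thus depends on the denominator, and the documents do not fix it for this case. Section 10.1.3 keeps every exposed subject in the safety analysis whenever eliminated. Section 10.1.5 restricts the main analysis to adherence of at least 75%, which a subject removed early would probably not reach. The documents also give no figure for how many volunteers have a known hypersensitivity. No magnitude can be derived.

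**The case against.** The strongest reply is that existing text already catches these people. Someone with a documented allergy to a required compound is arguably unable to comply with treatment and procedures. The anamnesis precedes staining, the procedure order is only suggested (7.4.1), and 5.4 foresees non-entry for an unlisted reason. The hypersensitivity bullets in 5.2 also do not say that a reaction must occur in the study, so hypersensitivity found on history could satisfy them.

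Much of this stands. A careful investigator would probably turn such a volunteer away. It does not remove the gap, because each route depends on interpretation and none states a bar. If 5.2 can be met on history alone, the same fact would leave a person eligible under 5.1 and eliminable under 5.2, which is itself a reason to reconcile them.

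Two stronger readings are tempting and unsupported:

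- A reader might infer that subjects are bound to receive the dyes before anyone can know their history, because the eligibility review is listed after staining. The anamnesis is listed earlier, and the final review sits late because it needs examination results such as intraocular pressure, which 7.3.3.1 has measured after the stains.
- A reader might infer from 2/22 = 9.1% that one avoidable reaction consumes half of the events the 10% rule tolerates. That needs a subject with known hypersensitivity to enrol, react, have the reaction attributed to PRO-172 and have it coded as unexpected. Reactions to a dye, the anaesthetic or a mydriatic do not count unless misattributed. A mild reaction to the product might be recorded as ocular itching or eye irritation, both on the expected list in 7.3.3.1. Known bepotastine allergy is likely to be very rare at this centre, since the protocol describes the drug as used in other countries.

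**Conclusion.** The point holds as a safety gap in the eligibility criteria: 5.1 and the synopsis do not exclude a known history of what 5.2 treats as disqualifying, so a volunteer with a documented reaction is not clearly ineligible. It is more than missing detail, because following the eligibility step as written could expose a healthy person to an identifiable and avoidable risk. It is small in frequency: few volunteers will be affected, and good site practice would stop some of them.

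The conclusion rests on the eligibility lists being complete as published and on the criteria being applied in their ordinary sense. It does not rest on any effect on the 10% criterion. That effect is conditional and unquantified, and should not be given as a reason for the change.

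**What to change.** Reconcile 5.1.2 and the synopsis with 5.2 by adding one exclusion to both lists, for example: known hypersensitivity to bepotastine, to any component of PRO-172, or to any compound used in study procedures (fluorescein, lissamine green, tetracaine, and tropicamide/phenylephrine if mydriasis is used). In 7.4.1.1, add a sentence stating that this criterion is checked from the anamnesis before any drop is instilled. The rest of the eligibility review can stay where it is.

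The cost is one line in two places and one sentence. The anamnesis is already taken at baseline, so no procedure is added. The downside is the loss of very few otherwise eligible volunteers. Dose, schedule, sample size and analysis are unaffected.

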
Primary outcome variables
 
 
- Incidence of unexpected AEs related to the investigational product. (Evaluation Time [ET]: days 8 and 10)
 
- ICO score (TE: day 8).
 
 
Secondary outcome variables:
 
 
- Changes in Corrected Visual Acuity (CCVA) (TE: day 8).
 
- Changes in corneal and conjunctival staining with lissamine green (TE: day 8).
 
- Corneal and conjunctival staining changes with fluorescein (TE: day 8).
 
- Conjunctival hyperemia changes (TE: day 8).
 
- Incidence of chemosis (TE: day 8).
 
	
Statistical methodology	

Data will be expressed using measures of central tendency: mean and standard deviation for quantitative variables. Qualitative variables will be presented as frequencies and percentages. Statistical analysis will be performed using the Wilcoxon rank test for quantitative variables. Differences between qualitative variables will be analyzed using the X (Chi-square) test or Fisher's exact test.
 
An <math>\alpha \leq 0.05</math> will be considered significant.
	

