## 5.6 Procedure in case of loss of tracking

For this protocol, loss to follow-up is defined as those subjects who were randomized, who at some point they were active subjects in the study, but their final evaluation could not be completed.

In the event that the participating subject does not attend his appointment, the research center must make a call to find out the reason and will try to arrange a new appointment within the established window period or a unscheduled appointment. If an appointment cannot be made, the presence of a adverse events and reason for withdrawal from the study, as minimum data.

A loss to follow-up <10% is not considered to be a problem for the validity of the studies. results obtained. [31, 32]

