$P_i$  = weight of the container delivered to the subject at the start

$P_f$  = weight of the container returned by the subject

$P_T$  = weight of the dosage indicated for the intervention

$$P_T = (P_g)G$$

Where:

$P_g$  = weight of a drop of the intervention, determined by the research and development department

G = number of applications indicated for the intervention

Packaging that does not maintain its physical integrity will not be considered for the calculation of adhesion.

For cases where the packaging is not returned, or it has not retained its physical integrity, the adherence through the subject's diary, as follows:

$$Ad = (A_r)100/A_i$$

Ad = Adhesion

$A_r$  = Registered applications

$A_i$  = Applications indicated for the intervention

The research center will designate a person in charge of monitoring adherence through the diary, during visits. Measuring adherence by weight will be the sponsor's responsibility.

There is no standardized parameter to define adequate adherence, it must be defined and delineated by the objectives of the particular research.[40]

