### 7.3.3.1 Adverse events

As defined in section 8.2, an AE is any unfavorable medical occurrence in a subject who is administer a PI, regardless of causal attribution.

The management of AEs will be carried out as described in the Adverse Events section.

The IP will record in the corresponding section of the electronic case report form (eCRF).

in English Case Report Form) the AEs that the subjects of the study may present in addition to referring to it in the medical record.

For an adequate evaluation of the EA, in addition to the directed questioning, it is necessary to carry out in each Visit the Comprehensive Ophthalmological Evaluation which consists of: the ophthalmological examination of the eyelids and annexes; anterior segment and posterior segment that is performed in a routine ophthalmological examination, whose procedures are not specifically included in the study variables. The evaluation of pole posterior may be with direct or indirect ophthalmoscopy, with or without pharmacological mydriasis, at the discretion of the IP.

An evaluation of the fundus will be performed to look for abnormalities that could alter the results of the study.

The IOP will be measured in this evaluation, with the instrument of the IP's choice, it should be measured after the evaluation of the stains. The result of the assessment will be recorded in the clinical record. In the eCRF only Findings that are considered as such by the IP will be reported as AEs.

According to the available literature, the expected AEs for the use of PI are: dysgeusia, eye irritation, Headache, nasopharyngitis, dry eye, ocular itching, nasal congestion and rhinorrhea.[42]

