### **7.3.3.2 ICO Score**

The ICO is a questionnaire designed to measure ocular surface irritation with Rasch analysis for produce estimates on a linear interval scale (scores: 0-100). Similar to the index for Ocular surface diseases, the Ocular Comfort Index (OCI) assesses symptoms. The OCI contains items that focus on the discomfort associated with ocular surface alterations. Each of these The questions have two parts, which separately inquire about the frequency and severity of symptoms.[43]

The evaluator will give the questionnaire to the subject and allow him to answer it calmly without any kind of pressure and/or coercion, will only assist you if you have difficulty understanding any of the questions.

Management as AE: The ICO assesses symptoms, which may or may not be related to an AE. The score obtained from the ICO alone, should not be considered an EA.

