#### **7.3.3.4 Corneal and conjunctival staining with fluorescein**

A drop of topical anesthetic will be instilled in the conjunctival fornix, then a drop will be applied. second drop on the tip of the fluorescein strip allowing it to sit on the strip for 5 seconds to elute the dye, shaking off the excess at the end. A small contact of the strip with the conjunctiva is made in the temporal fornix, while the patient looks up, without damaging the conjunctiva. It will be classified as according to the Oxford scale.[45]

The PI will record in the file and the eCRF the grade awarded for fluorescein staining of OD and OS respectively.

Management as AE: Corneal staining that is equal to or greater than grade III will be considered as AE.

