#### **7.3.3.6 Conjunctival hyperemia**

Conjunctival hyperemia is defined as the simplest reaction of the conjunctiva to a stimulus, it is seen a red appearance secondary to vasodilation of the conjunctival vessels of varying intensity. It will be graded using the Efron scale. [46] See appendix.

Management as AE: Conjunctival hyperemias classified as grade 3 or higher will be considered as AE. superiors.

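### No ICO or ocular-sign grading is required when a subject stops PRO-172 for intolerance, and two population rules conflict on whether early stoppers' ICO values are analysed

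*Protocol*

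**What the plan says.** **Stopping.** Protocol 5.2 lists "Non-tolerability or hypersensitivity to any of the investigational drugs" among the grounds for elimination and attaches no assessment to it.

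**Outcomes.** Tolerability is a specific objective measured by the ICO (3.2), which is one of two primary outcomes (7.3.1). The ICO, the staining grades and the hyperemia grade are taken at baseline and at the day-8 final visit only (7.3.1 to 7.3.3; SAP Table 1). The day-10 call covers adverse events.

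**Other contact.** Unscheduled visits are optional and must collect adverse event data (7.4.2). After a missed visit the centre tries to rebook. If it cannot, it records "adverse events and reason for withdrawal from the study, as minimum data" (5.6).

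**Populations.** Section 10.1.3 puts every exposed subject in the safety assessment, whenever they were eliminated. Section 10.1.5 admits to the analysis for the study objective only subjects with at least 75% adherence by bottle weight. In 6.4 the denominator of that percentage is the "weight of the dosage indicated for the intervention", computed as the weight of one drop times the number of applications, G. The SAP abbreviates both an intention-to-treat and a per-protocol set but defines neither. Its triangulation table (7.0) groups the ICO with adverse events under Security.

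**Adverse events.** Section 7.3.3.1 says "the expected AEs for the use of PI are: dysgeusia, eye irritation" and goes on to include dry eye and ocular itching. An ICO score alone "should not be considered an EA" (7.3.3.2). For marked signs, "Corneal staining that is equal to or greater than grade III will be considered as AE" (7.3.3.4), and "Conjunctival hyperemias classified as grade 3 or higher will be considered as AE" (7.3.3.6).

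**The concern.** For a subject who stops because the drop is uncomfortable, the reason for stopping is the quantity that the ICO is meant to measure. If that subject has no day-8 ICO, or has one that is set aside for low adherence, the ICO summary describes mainly the subjects who kept dosing.

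The other primary outcome covers only part of the gap. Irritation, dry eye and itching are on the expected list, so a stop for one of them would generally not count as an unexpected event. What can be lost is symptom burden and ocular signs below the adverse event thresholds. With 22 subjects and no comparator, one or two omitted stoppers can move the mean.

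**Working it through.** **1. What a stopper must provide.**

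| Route | Required data | ICO or grades required? |
|---|---|---|
| Elimination (5.2) | none stated | no |
| Unscheduled visit (7.4.2) | adverse event data | no |
| Missed visit, not rebooked (5.6) | adverse events, reason for withdrawal | no |
| Final visit, if attended (7.4.1.2) | full set | yes |

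The general eye examination in 7.3.3.1 does not fill the gap, because it covers procedures outside the study variables. Section 10.1.3 keeps a subject in the set but gives no rule for a missing ICO.

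**2. The adherence cut.** The plan's own figure is 75%. Dosing is one drop in each eye, four times a day for 7 days (6.1.3): 28 dosing times, 56 drops. Assume full dosing up to the last dosing day s, nominal drop weight and no waste. The weight used is then 8s drops.

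- Reading A: G = 28 dosing times, one drop weight each. Adherence = 8s/28.
- Reading B: G counts both eyes, so G = 56. Adherence = 8s/56.

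| Last full dosing day | A | B |
|---|---|---|
| 2 | 16/28 = 57% | 16/56 = 29% |
| 3 | 24/28 = 86% | 24/56 = 43% |
| 4 | over 100% | 32/56 = 57% |
| 5 | over 100% | 40/56 = 71% |
| 6 | over 100% | 48/56 = 86% |

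Under A, stops through about day 2 fall below 75%. Under B, stops through about day 5 do. Reading A follows the formula literally, but a fully adherent subject would then score 56/28 = 200%, so the intended count is unclear. Drop weight also matters. Under B, a day-5 stopper passes if drops run 5% heavy (0.75/0.714 = 1.05), so day 5 is borderline. A day-4 stopper needs drops 31% heavy (0.75/0.571 = 1.31).

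**3. Chance of any intolerance stop.** The documents give no stop rate, so p is an assumption. P(at least one of 22) = 1 - (1 - p)^22.

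| p | 1% | 2% | 5% | 10% |
|---|---|---|---|---|
| P(at least one) | 20% | 36% | 68% | 90% |

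**4. Shift in the mean ICO change.** Let k of 22 subjects stop and be left out. Stoppers rise by d points and completers change by m. The full mean is m + k(d - m)/22 and the completer mean is m, so the understatement is k(d - m)/22. All three inputs are assumptions.

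| | m = 0 | m = 3 |
|---|---|---|
| k = 1, d = 5 | 0.23 | 0.09 |
| k = 2, d = 20 | 1.82 | 1.55 |
| k = 3, d = 30 | 4.09 | 3.68 |

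**5. Effect on the planned Wilcoxon test.** In an illustrative simulation, completers change by 0 on average, stoppers by +25, and both have SD 8 (all assumed). The chance of a significant worsening at 0.05, with stoppers included against excluded, was 3.6% against 2.1% for one stopper, 7.0% against 2.3% for two, and 19.8% against 2.4% for four. With one or two stoppers the reported mean moves more visibly than the test result.

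**The case against.** The strongest reply has four parts.

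*The ICO is already a safety variable.* The SAP's triangulation table places it with adverse events, and protocol 3.3 frames the ocular signs as safety objectives. On that reading 10.1.3 keeps every available value. This has force. It does not settle the matter, because 10.1.5 governs the analysis for the study objective, which is safety and tolerability (3.1, 3.2). Nor does it supply a value that was never collected.

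*Nothing cancels the day-8 visit.* This is correct. Section 5.6 directs rebooking before the fallback applies. A reader might infer that the plan discards stoppers' ICO by design, but the documents do not say so. They only fail to require it.

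*Intolerance stops remain visible.* The reason for withdrawal (5.6) and drug withdrawal with its outcome (8.4.1) are recorded. Grade III corneal staining, grade 3 hyperemia and a loss of more than two Snellen lines are adverse events. Hypersensitivity is not on the expected list. The only definition of unexpected (8.5, for unanticipated problems) includes severity and frequency, so a severe irritation could qualify. This narrows the gap to ordinary discomfort and lower-grade signs.

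*No decision depends on it.* The plan sets no ICO threshold, so a shift of a few points has no benchmark. The upper end of the range needs three stoppers. P(3 or more of 22) is 0.9%, 9.5% and 38% at stop rates of 2%, 5% and 10%. This limits the importance of the point but does not remove it, since the ICO is a declared primary outcome.

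**Conclusion.** The point holds as a gap with a probable direction and an unknown size. The plan does not secure the tolerability outcome for subjects who stop for intolerance, and its two population rules conflict on whether early stoppers' ICO values count. For stops due to drop discomfort, the ICO summary may lean toward good tolerability. Stops for dye or tetracaine reactions, or for unrelated serious events, have no fixed direction. The range of 0.2 to 4.1 points (m = 0) rests wholly on assumed numbers of stoppers and score changes.

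Two stronger readings are tempting. One is that anyone stopping by day 5 is removed. That needs 10.1.5 to govern and G to count both eyes; with G = 28, removal ends at about day 2. The other is that the study's conclusion is biased. The safe-and-tolerable verdict in 10.1.5 uses only unexpected related adverse events and does not depend on the ICO. This is a cheap improvement that leaves the formal criterion as it is.

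**What to change.** 1. **Protocol 5.2 and 7.4.2:** for anyone who stops PRO-172 without withdrawing consent, bring the final-visit assessments forward to the stopping visit, with the ICO first and before any drops. Keep the day-10 call.
2. **Protocol 10.1.3 and SAP 7.0:** use those values as post-treatment values in the ICO and ocular-sign analyses for all exposed subjects, and report the number of intolerance stops beside the ICO result. If an ICO is still missing, assign the worst rank as a sensitivity analysis only.
3. **Protocol 10.1.5:** state that 10.1.3 governs the ICO and ocular signs, so that the 75% cut does not remove subjects who stopped for intolerance or an adverse event.

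The clinical criteria for stopping stay as they are. The cost is wording in two documents and earlier final-visit procedures for a few subjects. The sample size does not change.

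The repair is partial. Exposure lengths will be mixed, and the ICO asks about the past week. After a last dosing day s, the recall window at the stopping visit holds about s exposed days of 7 (2 of 7 for a day-2 stop) and is otherwise pre-drug. Waiting does not help: a day-8 visit also covers about s exposed days, and a day-9 visit about s - 1.
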